Primary Endpoint: Estimation of required sample size for a later RCT through calculation of effect size for change in body mass index (BMI) from baseline to 16 weeks of liraglutide.

Key Secondary Endpoints:

Changes in BMI and fat mass after 16 weeks of liraglutide

Comparison of changes in BMI and fat mass after 16 weeks of liraglutide in participants who had a poor initial response to SG (<20% BMI reduction at BMI nadir) vs. those with a typical post-SG weight loss ($\geq 20\%$ BMI reduction at BMI nadir)

Tolerability and safety of liraglutide 3.0 mg.

Additional (exploratory) Endpoints: Change from baseline to 16 weeks of liraglutide in:

1. Proportion reducing BMI by at least 5% and 10%
2. BMI standard deviation score for age and sex (BMIZ)
3. Body weight
4. Percentage total body fat mass by DXA
5. Appetite score using visual analog scale (VAS)
6. Attention bias to highly palatable images
7. Energy intake at buffet meal
8. Free living physical activity by accelerometry
9. Metabolic syndrome markers (waist circumference, systolic and diastolic blood pressure, lipids, fasting plasma glucose level)
10. Fasting plasma insulin and HOMA-IR index
11. 2-hour oral glucose tolerance test (OGTT) insulin and glucose measurements
12. Hemoglobin A1C
13. Plasma GI hormones (GLP-1 and PYY) during OGTT
14. Weight related quality of life (QoL) score
15. Beck Depression Inventory total score
16. Body-Esteem Scale Score for Adolescents and Adults
17. Columbia Suicide Severity Rating Scale
18. Secretome analysis
19. Stool microbiome analysis

Study Population:

Up to a total of 50 male and female adolescents age < 21 years old from Washington D.C., Maryland, and Virginia who underwent SG at least 1 year prior to enrollment and have BMI ≥ 30 kg or $\geq 95^{\text{th}}$

Abbreviated Title: Liraglutide in Teens Post-SG

Version Date: 1/30/23

percentile for age and sex in order to enroll at least 40 who are eligible and agree to take liraglutide for 16 weeks.

Phase:

Phase II

Description of Sites/Facilities

We will primarily recruit participants who previously underwent SG from Children's National Hospital (CNH), in Washington, DC, a high-volume pediatric bariatric surgery center in our area.

Enrolling Participants:

Participants will be assessed at the NIH Clinical Center for all study visits. Eligible participants may also be interviewed by telephone.

Description of Study Intervention:

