Visits 2-4: Each participant will undergo a brief history and directed physical examination to include injection site examination at monthly visits. Weight, height, and blood pressure will be measured at each visit. All participants will be assessed for adverse effects of study drug. Female participants will undergo a repeat pregnancy test at every visit. All participants will meet with Nutrition Staff to receive standardized education on a healthy diet. Used 1-month supply of liraglutide pens will be returned to research team and new 1-month supply of liraglutide will be provided to participant. At visit 4, a wrist accelerometer to measure free living physical activity will be placed and testing on attention bias to highly palatable images will be conducted. They will also receive material to collect stool at home if they choose to turn in stool samples at Visit 5.

Visit 5 (at ~16 weeks): Each participant will undergo a history and physical examination and female participants will undergo a pregnancy test. All participants will then undergo fasting blood work followed by 2-hour oral glucose tolerance testing, questionnaires, testing on appetite, DXA scan, and energy intake measurement at a buffet meal at the NIH Clinical Center. They will meet with Nutrition Staff to review their 1-week food log and receive standardized education on a healthy diet and physical activity. Each participant will have the option to turn in stool samples collected at home or during their clinic visit. Used 1-month supply of liraglutide pens will be returned to research team. Liraglutide will be discontinued at this visit. The wrist accelerometer will be returned.

Visit 6 (off medication, at ~28 weeks): Each participant will undergo a history and physical examination. Weight, height, and waist circumference will be measured.

Abbreviated Title: Liraglutide in Teens Post-SG

Version Date: 1/30/23

INTRODUCTION

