1.17.2 Dosing and Administration

1.17.2.1 Dose Escalation

Table 1: Titration Schedule for Liraglutide

Study schedule	Week	Liraglutide (subcutaneous injection)
Screening	-1 to 0	-
Baseline visit	0-1	0.6 mg once daily as tolerated
	1-2	1.2 mg once daily as tolerated
	2-3	1.8 mg once daily as tolerated
	3-4	2.4 mg once daily as tolerated
Target study dose	4-16	3.0 mg once daily as tolerated

The participant will start the study drug at Visit 1 (Baseline Visit) after the History & Physical Examination. The study drug will be titrated to the highest tolerable dose as per Table 1 above.

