Free living physical activity and sleep by accelerometry: Participants will be asked to wear an accelerometer on their body that measures free-living physical activity. The participant will be instructed to wear the accelerometer during all hours, except when bathing or showering for 2 weeks and to return the accelerometer in person or via mail after completion. We will use the ActiGraph GT3X+ activity monitor (ActiGraph, Pensacola, FL), which is worn like a wristwatch and delivers 24-hour physical activity and sleep/wake measurements. We have used this device successfully in other protocols with adolescents (15-CH-0096) [76, 77]. Outcomes include raw acceleration, activity counts, energy expenditure, physical activity intensity, body position, and sleep duration. A triaxial accelerometer and integrated ambient light sensor assist with enhancing the validity of data collected regarding sleep/wake times. The GT3X+ can store over 40 days of raw data, and its rechargeable battery is capable of providing power for 30 days between charges. Data will be downloaded and reduced using Actilife software (ActiGraph). In young adults, the GT3X+ is a valid and reliable device for detecting sleep/wake diurnal patterns, and has demonstrated good concordance with polysomnography [78]. The GT3X+ wrist actigraphy has also been used to assess sleep behavior in adolescents [79, 80].

Patient questionnaires:

Quality of life assessments-

Impact of Weight on Quality of Life-Lite (IWQOL-Lite)[81]

The IWQOL-Lite is a validated 31 item self-report measure of obesity-specific quality of life questionnaire. The IWQOL-Lite provides a total score inclusive of 5 domains: physical function, self-esteem, sex life, public distress, and work. The questionnaire is responsive to weight loss and gain, sensitive to treatment seeking status as well as to the degree of obesity. The IWQOL-Lite will be conducted in participants ≥ 18 years of age according to the SOA.

Abbreviated Title: Liraglutide in Teens Post-SG

Version Date: 1/30/23

The Impact of Weight on Quality of Life (IWQOL)-Kids version for adolescents [82] will be used in all patients in this study.

SF-10 Health Questionnaire for Children

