The Body-Esteem Scale for Adolescents and Adults is a 23-item measure with subscales of general feelings regarding own's own appearance, one's perception of others' evaluation about one's body and appearance, and weight satisfaction [86]. Responses regarding agreement with item statements are provided on a 5-point Likert scale ranging from never (1) to always (5) with higher scores indicating more positive body-esteem.

Diet and Nutritional Counseling

Abbreviated Title: Liraglutide in Teens Post-SG

Version Date: 1/30/23

Nutritional counseling and monitoring will be performed by nutrition department staff. Nutrition department staff will review food log with participants.

Order of Assessments

When scheduled at the same time point, the order of procedures should be as follows: obtain vital signs, perform history and physical examination, perform blood testing (at the specified time point, if applicable), perform DXA scan, perform computerized visual probe task of sustained attention, have participant answer questionnaires, and eat buffet meal (measure appetite score before and after). Adjustments may be made depending upon specific circumstance.

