1.33.9 Exploratory Analyses

Any of the exploratory evaluations that generate quantitative measures will be examined using descriptive statistics including confidence intervals when appropriate. Any statistical tests (paired t-tests of baseline versus 16-week results) performed for evaluation of exploratory objectives will be done without formal adjustment for multiple comparisons, but in the context of the number of tests performed.

The following dependent variables will be examined in the dataset:

Change in: BMI standard deviation score for age and sex, body weight, percentage total body fat mass by DXA, appetite score using visual analog scale, attention bias to highly palatable images, energy intake at buffet meal, free living physical activity by accelerometry, hemoglobin A1C, plasma GI hormones (GLP-1 and PYY), weight related quality of life score, Beck depression inventory total score, Columbia-Suicide Severity Rating Scale, body-esteem scale score for adolescents and adults, HOMA-IR, fasting glucose and insulin, triglycerides, LDL- and HDL-cholesterol, OGTT glucose and insulin AUC, SomaScan platform.

REGULATORY AND OPERATIONAL CONSIDERATIONS

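### Attention bias and free-living activity are defined and tested as 16-week outcomes, but the schedule collects them at about week 12 and weeks 12 to 14

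*Combined protocol and SAP*

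**What the plan says.** **Endpoint definition.** In section 1.1 (Synopsis) the exploratory list opens with "Additional (exploratory) Endpoints: Change from baseline to 16 weeks of liraglutide in". Item 6 is "Attention bias to highly palatable images" and item 8 is "Free living physical activity by accelerometry".

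**Analysis.** Section 1.33.9 names both among the variables to be examined as changes, and describes the tests as follows: "Any statistical tests (paired t-tests of baseline versus 16-week results) performed for evaluation of exploratory objectives".

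**Collection.** The visit descriptions under section 1.3 put the baseline attention-bias test and accelerometer set-up at the Screening Visit, with the device handed back at Visit 1. On treatment, the text reads "At visit 4, a wrist accelerometer to measure free living physical activity will be placed and testing on attention bias to highly palatable images will" take place. The Visit 5 description lists blood work, OGTT, questionnaires, appetite testing, DXA and the buffet meal. It includes no attention-bias test, and the accelerometer is only returned.

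**Wear time.** Section 1.26.1 tells participants to "wear the accelerometer during all hours, except when bathing or showering for 2 weeks".

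**Visit timing.** The schedule table in section 1.3 gives Visit 4 as Day 84 and Visit 5 as Day 112, each with a window of 10 days either side.

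**The concern.** The endpoint definition and the test both require a 16-week value. For attention bias the schedule never produces one. For activity it produces a two-week record that nominally closes before week 16. No section gives an analysis window assigning Visit 4 data to week 16. An analyst following the plan would therefore either find no 16-week attention-bias value or use Visit 4 data under a 16-week label. Readers would then take a result from about 12 weeks of treatment (12 to 14 for activity) as a result after 16 weeks. This affects every participant, and a test not done at Visit 5 cannot be recovered afterwards.

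**Working it through.** **Inputs.** Visit 4 is Day 84 ± 10 and Visit 5 is Day 112 ± 10 (section 1.3 table). Accelerometer wear is 14 days from placement (section 1.26.1).

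**1. The plan's own figure.** Week = day / 7. Visit 5: 112 / 7 = 16.0, which agrees with the visit text placing it at about 16 weeks. With the window: 102 / 7 = 14.6 to 122 / 7 = 17.4.

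**2. Attention bias.** Visit 4: 84 / 7 = 12.0 weeks. With the window: 74 / 7 = 10.6 to 94 / 7 = 13.4.
- Nominal gap to Visit 5: 112 − 84 = 28 days.
- Smallest gap the windows allow: 102 − 94 = 8 days.
- Largest: 122 − 74 = 48 days. This pairs opposite window limits, so it is a bound and not an expectation.

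Because the smallest gap is positive, no Visit 4 test can fall inside the Visit 5 window.

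**3. Activity.** The wear interval runs from the Visit 4 day to the Visit 4 day + 14.

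| Visit 4 | Wear (days) | Weeks | Days inside Visit 5 window (from Day 102) | Days from end of wear to Day 112 |
|---|---|---|---|---|
| Earliest, Day 74 | 74–88 | 10.6–12.6 | 0 | 24 |
| Nominal, Day 84 | 84–98 | 12.0–14.0 | 0 | 14 |
| Latest, Day 94 | 94–108 | 13.4–15.4 | 6 | 4 |

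Only a late Visit 4 brings part of the record into the Visit 5 window, by at most 108 − 102 = 6 of 14 days.

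**4. Is this a fault of table extraction?** The column alignment of the extracted schedule cannot be trusted on its own: read literally, it puts baseline attention bias under the phone screen, against the visit text. The finding therefore rests on the visit descriptions, which name Visit 4 in words. The table is consistent with them, since the on-treatment marks for these two rows sit one column before those for DXA, the buffet meal and the questionnaires.

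**5. Baseline wear.** Table 1 in section 1.17.2.1 shows screening as week −1 to 0, which is 7 days and shorter than the 14-day wear. Section 1.25.2 allows screening procedures within 28 days before enrollment, which leaves 28 − 14 = 14 days to spare.

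**The case against.** Several points on the other side have force.

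- **Activity is not measured at Visit 4 itself.** The device is placed there, and any wear period must begin before the visit it informs. This stands, and makes the mismatch smaller for activity than for attention bias. It does not remove it: nominal wear stops 14 days short of Day 112, and nothing asks participants to keep the device on until Visit 5.
- **The endpoints are exploratory and the testing is conditional.** Section 1.33.9 speaks of any tests performed, without multiplicity adjustment, and the tertiary list in the Objectives and Endpoints table states no time frame. This limits the consequence. The synopsis and section 1.33.9 still say 16 weeks.
- **Carrying values forward might supply week 16.** Section 1.33.3 uses LOCF for the secondary endpoints and says tertiary endpoints follow similar approaches. That rule is stated for missing data. Applied here it would turn every attention-bias value into a carried-forward one, and no section says this is intended.
- **The placement may be deliberate.** Both measures fall at the visit before each long assessment day. That is plausible, and it favors correcting the label over moving the task.

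A reader might also infer more than the documents support:

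- **That the protocol already assigns the task to Visits 1 and 5.** The order-of-assessments text in section 1.26.1 runs "perform DXA scan, perform computerized visual probe task of sustained attention, have participant answer questionnaires, and eat buffet meal", but it governs only procedures that share a time point and allows adjustments. It schedules nothing.
- **That a link between attention bias and energy intake is lost.** The objectives table offers that link as a reason for measuring attention bias. No analysis relating the two is planned.
- **That baseline activity would be cut in half or run past the first dose.** The 28-day screening window leaves room for two weeks of wear. The device comes back at Visit 1, where the first dose is given at the end of the visit.
- **That the estimates would be biased by a known amount.** Nothing in the documents shows that either measure differs between weeks 12 and 16. The defect is in what the result is called.

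**Conclusion.** The inconsistency is real and should be corrected, though its reach is narrow. For attention bias it is complete: the only on-treatment test is at about week 12, nominally 28 days before Visit 5 and never within the Visit 5 window, so no 16-week value exists. For activity it is partial: the data nominally cover weeks 12 to 14, and only a late Visit 4 brings up to 6 days of wear into the Visit 5 window. Results reported under the present wording would be mislabelled for these two exploratory endpoints. The primary endpoint and the BMI and fat-mass analyses are unaffected, and no sample-size or power figure depends on these measures. The conclusion assumes that visits keep to their windows and that wear stops after the two weeks instructed.

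**What to change.** Make the synopsis, section 1.33.9 and the schedule agree in one of two ways.

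1. **Relabel.** In the synopsis and section 1.33.9, define attention bias as the change from the screening baseline to about week 12, and activity as baseline versus about weeks 12 to 14. State the paired tests in the same terms. This is a wording change only and resolves the inconsistency in full.
2. **Realign, if 16-week values are wanted.** Schedule the existing attention-bias task at Visit 5, and time the existing 14-day wear to end at Visit 5, with a nominal start of Day 112 − 14 = Day 98. No new procedure is needed. The costs are a longer Visit 5, which already carries the OGTT, DXA and buffet meal; a rule for where the food-image task falls relative to the glucose load and the meal; and an arrangement for starting wear between visits.

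As a minor tidy-up, reconcile the screening entry in Table 1 (week −1 to 0) with the 28-day screening window and the two-week wear period, so that the time available for the baseline record is clear.

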1.4 STUDY RATIONALE

Obesity is a global epidemic that is associated with multiple co-morbidities and disability in both children [1] and adults. In the United States, in 2015-2016 [2], 20.6% of children and adolescents age 12-19 years had obesity (defined as $\text{BMI} \geq 95^{\text{th}} \text{ percentile}$ for age and sex for the Centers for Disease Control standards [3]) and 7.7% had severe obesity ($\text{BMI} \geq 120\%$ of the 95^{th} percentile) [2]. Obesity-related diseases previously rare in adolescents [4-6] including type 2 diabetes [7-10], are increasingly diagnosed, with those having rapid early weight gain most at risk [11, 12]. The appearance of obesity-associated conditions in childhood leads to an earlier onset of related medical complications [13-15]; severe obesity also increases risk from COVID-19 infection [16-19]. Some [20-22] though not all [23-25] studies suggest pediatric obesity has a unique impact on later health, even independent of adult weight; Regardless, there is unanimity that adolescent obesity is a strong risk factor for persistence into adulthood and medical complications. Without effective strategies to treat adolescent obesity, millions of adolescents will enter adulthood with the physical and psychological consequences of excess adiposity. Adolescent obesity also has the potential to reverse the improvements in life-expectancy that occurred during the 20th century in the U.S [26, 27] and to cause more functional disability in those who survive to old age [28].

Initial management of obesity involves making lifestyle modifications to increase physical activity and adopt a healthy and well-balanced diet. However, most adolescents achieve only mild to moderate weight loss with reduction of BMI by -1 to -2 kg/m² and have difficulty implementing and sustaining their lifestyle changes [29]. Adolescents who continue to have severe obesity or have obesity with complications such as sleep apnea or diabetes despite lifestyle modification are sometimes prescribed pharmacologic agents, but options are limited; Orlistat, a lipase inhibitor is FDA approved for children ≥ 12 years, and phentermine, a norepinephrine reuptake inhibitor for short-term use (12 weeks) is FDA approved for adolescents > 16 years [30, 31]. Both have modest efficacy with approximately 3% mean BMI reduction [30, 31]. Liraglutide, a glucagon-like peptide 1 (GLP1) agonist is the latest medication to be approved for chronic weight management in children 12 years and older with $\text{BMI} \geq 30 \text{ kg/m}^2$. A double-blind, placebo-controlled phase 3 study showed that after 56 weeks, patients treated with liraglutide achieved a statistically significant reduction in BMI SDS of -0.23 compared with no reduction in the placebo group (estimated treatment difference: -0.22; 95% CI, -0.37, -0.08; P =.0022) [32].

Other agents have also been used off-label in some pediatric patients with variable results and unknown long-term outcomes. Consequently, an increasing number of patients with moderate to severe obesity and its comorbidities who fail to lose weight despite lifestyle and pharmacologic intervention are undergoing metabolic and bariatric surgery (MBS), which is currently considered the most effective treatment of severe obesity and its associated comorbidities, and is recommended by both the American Society for Metabolic and Bariatric Surgery (ASMBS) and the American Academy of Pediatrics (AAP) [33, 34].

The two most common surgical approaches used in children and adolescents with obesity are sleeve gastrectomy (SG) and Roux-en-Y gastric bypass (RYGB). In 2015, 66.6% of cases were SG and 28.5% were RYGB among adolescents age 18-21 years who underwent MBS in the

Abbreviated Title: Liraglutide in Teens Post-SG

Version Date: 1/30/23

United States[35]. SG involves removal of 80-90% of the greater curvature of the stomach and achieves weight loss by restricting food intake whereas RYGB entails creating a small gastric pouch from the upper stomach that is connected directly to the middle portion of the small intestine (jejunum), bypassing the rest of the stomach and the upper portion of the duodenum. RYGB induces both restriction and changes in absorption. Both SG and RYGB have also been proposed to alter the metabolic/humoral milieu to reduce drive to eat [36].

Weight loss occurs rapidly following RYGB and SG and generally reaches a peak by 12 months postoperatively. The Teen-Longitudinal Assessment of Bariatric Surgery (Teen-LABS) study, the largest prospective multi-center observational study to date in pediatrics with 242 adolescents (≤ 19 years of age, mean BMI of 53) showed that among 67 patients who had SG, BMI decreased from 50 kg/m^2 at baseline to 37 kg/m^2 (26% reduction) and among 161 patients who had RYGB, BMI decreased from 54 kg/m^2 at baseline to 39 kg/m^2 (28% reduction) three years post-operatively [37]. Thus, although most patients experienced significant weight loss with a 26 to 28% reduction in BMI following MBS, 75% still met criteria for obesity (BMI $>30 \text{ kg/m}^2$; Figure 1). Furthermore, many patients experienced weight regain after reaching their weight nadir at approximately 1 year [37-41] that places them at continued risk for the metabolic consequences of obesity.

[figure not shown]

Figure 1: BMI at Baseline and Three Years After Adolescent Bariatric Surgery.

Adapted from [37]. Only 26% achieved BMI $<30 \text{ kg/m}^2$

To address how best to assist post-bariatric adolescents who continue to have obesity, we propose that the use of liraglutide, a glucagon-like peptide-1 (GLP1) agonist be studied in adolescent patients (age 12-20y) with BMI ≥ 30 or BMI $\geq 95^{\text{th}}$ percentile for age and sex, 1 year or more after SG, which is now the most common pediatric bariatric operation in the United States. Results from this drug trial, if positive, may help develop a new pharmacologic option for refractory adolescent obesity and an opportunity to investigate the mechanism of action of

Abbreviated Title: Liraglutide in Teens Post-SG

Version Date: 1/30/23

GLP-1 in treating children and adolescents with obesity post-bariatric surgery, a group uniquely resistant to treatment.

